3.7.3 Off Protocol Therapy and Off-Study Procedure

Authorized staff must notify Central Registration Office (CRO) when a subject is taken off protocol therapy and when a subject is taken off study. A Participant Status Updates Form from the web site (<http://home.ccr.cancer.gov/intra/eligibility/welcome.htm>) main page must be completed and sent via encrypted email to: NCI Central Registration Office [contact].

3.7.3.1 For Participating Sites

The Participant Status Updates Form will be supplied by the NCI study coordinator. Send the completed form to the NCI study coordinator.

3.8 FOLLOW-UP EVALUATIONS

After subjects have stopped taking the study medication for any of the reasons listed in Section [3.7](#), they will be seen at the study site, if logistically feasible, for a safety visit within 4-5 weeks of drug discontinuation. The safety assessments may be performed by a local physician and laboratory if patients unable to return to the study site at this time.

The following assessments will be performed at the follow up safety visit:

- History and Physical Examination
- Serum chemistries (Na+, K+, Cl-, CO2, glucose, BUN, creatinine, albumin, calcium, magnesium, phosphorus, alkaline phosphatase, ALT, AST, total bilirubin, LDH, CK, uric acid, total protein)
- CBC/differential with platelet count
- Serum PSA level
- Serum PAP
- Adverse event reporting

After the safety visit, if there are no unresolved grade 3 or higher AEs, we may, when feasible contact the patient annually to find out how they are doing and to determine survival status. If there are unresolved grade 3 – 4 AEs, patients will be followed either at the study site or by their local physician. In the latter case, we will obtain the physician's record of AEs.

Any scans performed outside of the study site will also be obtained when possible.

4 BIOSPECIMEN COLLECTION

4.1 CORRELATIVE STUDIES FOR RESEARCH

4.1.1 Immunologic Parameters

- Antibodies to PSA, vaccinia, fowlpox may be tested
- Leukocyte CD3, CD4, CD8 subsets; CD4:CD8 ratio will be drawn at baseline and monthly prior to vaccination while the patient remains on trial.
- The results of the HIV antibody need to be available before treatment to determine eligibility
- Additional studies will include but are no limited to quantitative and qualitative assessments of regulatory T-cells, Natural Killers cells, Myeloid Derived Suppressor Cells, anti-glycan antibodies and Naïve T-cell/new thymic emigrants.
- Assessment of levels of cytokines.
- Immunologic studies will be repeated more frequently if clinically indicated, and any abnormalities potentially related to treatment will be followed until they have resolved, or have been determined not to be treatment-related.

4.1.2 Immunologic Assays

4.1.2.1 CD4 T Cell Proliferation Assay

It is planned that all patients will undergo exploratory analysis of the ability to detect CD4-positive responses using a whole-protein PSA assay, as well as a peptide mix with 63 different 15-mer peptides by ELISPOT and/or ELISA.

4.1.2.2 Sera Antibody Analysis

Serum will be stored at -80 degrees Celsius and there will be planned analysis for generation of antibodies to PSA, BCG, PAP, PSMA, PSCA, and/or MUC-1.

4.1.2.3 Flow cytometry analysis of thymic emigrant

To determine recent thymic emigrants, flow cytometry analysis will be performed on peripheral blood mononuclear cells. Cells will be resuspended in staining buffer (phosphate-buffered saline containing 3% fetal bovine serum) and stained for 30 minutes at 4°C with the combination of following antibodies: APC-H7-conjugated anti-CD4, PE-CY7-conjugated anti-CD3; FITC-conjugated CD45RA, PE-conjugated CD31, PerCP-CY5.5-conjugated Ki-67, AF-700-conjugated-CD197, V450-conjugated CD8, APC-conjugated CD103, V500-conjugated CD27 all purchased from BD Pharmingen, San Diego, CA). After that, FoxP3 intra-cellular staining will be performed on the cells stained with anti-CD4 and anti-CD25. They will be fixed and permeabilized using a fix/perm kit (eBioscience, San Diego, CA) according to the manufacturer's manual, and will be labeled with FITC-conjugated anti-Foxp3 antibody (236A/E7 clone) or its isotype control antibody (eBioscience). Flow cytometry will be performed on a Becton Dickinson LSRII (BD Biosciences) device.

4.1.2.4 Natural Killer (NK) CELLS

The number and phenotype of NK cells will be determined by phenotypic analysis of PMBCs stained for CD56, CD3, CD8, and CD16 by flow cytometry.

4.1.2.5 Immune Subsets: Subsets of immune cells will also be followed in response to treatment.

4.1.2.6 Regulatory T Cells

Regulatory T cells have been shown to inhibit the activation and function of T cells that participate in antigen-specific immune responses. Higher levels of regulatory T-cells have been reported in the peripheral blood mononuclear cells of patients with several types of tumors. The number and phenotype of regulatory T-cells in peripheral blood mononuclear cells from patients in this study will be determined by 7-color flow cytometry analysis. Cells will be resuspended in staining buffer (phosphate-buffered saline containing 3% fetal bovine serum) and stained for CD4, CD25, CD127, FoxP3, CTLA-4, CD45RA, and CD8. The ratios between regulatory T-cells and CD4 effector cells and the ratios between regulatory T-cells and CD8 Effector cells will also be analyzed.

4.1.3 Additional Assays

Blood samples may be used for additional research studies, which may include phenotypic and functional analysis of immune-cell subsets and analyses for cytokines (IFN- γ , IL-10, IL-12, IL-2, IL-4, etc.), chemokines, antibodies, tumor associated antigens, and/or other markers

All samples will be labeled with the following identifier system.

- Patient's enrollment #
- Trial number
- Patient's initials

Example: 01-ABC

These labels are used only to send the samples from the NIH Clinical Center to the NCI Frederick Central Repository. The NCI Repository will process all samples, appropriately discard the label on the blood tube, and then store the samples with unique identifiers, to which only NCI study personnel will have the code to link to patient specific clinical information. Samples will be tracked according to Section [4.2](#).

If there are inadequate samples for analysis because of loss or destruction of those samples, the NCI PI will report this to the IRB.

4.1.4 For Participating Sites – Collection and Shipping of Research Blood Samples

For patients at participating sites, research samples consisting of 6 green top tubes and 2 red top tubes will be drawn at baseline, Cycle 1 Day 1, Cycle 2 Day 1, Cycle 6 Day 1, and Cycle 9 Day 1. The green top tubes will be sent via overnight Fed-Ex to the NCI Frederick Repository at the address below:

Leidos Biomedical Research
Attn: [name]

[name]
[name]
[name]
[contact] or [contact]

The red top tubes will be spun down and stored in a -80°C freezer at participating sites. These serum samples will be batched and then shipped to the NCI Frederick Repository (address above) at intervals.

Once a patient's treatment schedule has been determined, [name] at the Laboratory of Tumor Immunology and Biology/NIH should be notified at [contact] for planning purposes. Please see **APPENDIX F** for further details.

End of study research blood draw is optional for patients based on logistics and investigator discretion.

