Briefly, the methodology takes cryopreserved peripheral blood mononuclear cells (PBMCs) from patients before therapy and at the time of restaging. They are thawed and rested overnight at 37°C, 5% CO₂ in complete media (IMDM supplemented with 10% Human AB, 2mM glutamine, 100 units/ml penicillin, and 100 µg/ml streptomycin). The next day (Day 0), PBMCs are seeded in 12 well plates (2.5×10^6 in 1 mL), and stimulated with peptide mixes (0.1µg/mL per peptide); cultures were supplemented on days 3 and 5 with cytokines (IL7 and IL15, 10 ng/mL, PeproTech, Rocky Hill, NJ) and fresh media, and on day 7 are rested (with removal of cytokine and peptide). On day 11, 1×10^6 cells were restimulated for 24 hours in 96 well plates with peptide mixes in the presence of anti-CD107a-APC (clone H4A3, BD Biosciences); brefeldin A (1ul/mL) and monensin (0.7ul/mL) (BD Biosciences) are added to cultures 2 hours after the start of the restimulation and incubated for the final 22 hours. PBMCs are then stained with anti-CD4-PerCP-Cy5.5 (clone OKT4, Biolegend), anti-CD8-AF700 (clone OKT8, Ebioscience), and anti-TNF-PE (clone MAAb11), anti-IFN γ -PE-Cy7 (clone 4SB3), and anti-IL-2-BV521 (clone 5344.111) (BD Biosciences). At least 3×10^5 events in the live gate are acquired with a BD LSR-II flow cytometer equipped with a UV, violet, blue, and red laser. FCS files are analyzed with FlowJo V.9.7 for Macintosh (TreeStar, Ashland, OR). Fluorescence minus one (FMO) controls are used for gating, and non-viable cells were excluded. The absolute number of CD4 $^+$ or CD8 $^+$ lymphocytes producing cytokine or positive for CD107a is calculated per 1×10^6 cells plated at the start of the IVS. The background signal (obtained with the HLA peptide pool), and values obtained prior to therapy were subtracted from those obtained post-therapy. Values ≥ 250 are scored as positive for TAA-specific immune response following therapy. ([Figure 4](#))

[figure not shown]

Figure 4: Methodology of Assessing PSA-specific Immune Responses

Flow Cytometry Analysis of Immune subsets (Biomarker Development)

As part of the extensive immune interrogation, peripheral immune cells will be evaluated by 30 markers to assess 127 immune subsets. ([Table 2](#)) This methodology has been previously described.¹⁵ This added analysis will provide preliminary data to develop a Peripheral Immunoscore based on the frequency of specific pre-determined immune cell subsets in the

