2.3.2 Treatment Assignment and Randomization Procedures

Cohorts

Number	Name	Description
1	Prostate Cancer	Male patients diagnosed with prostate cancer (non-metastatic), with demonstrated biochemical progression, a PSA doubling time of 5-15 months, and with a rising PSA.

Arms

Letter	Name	Description
A	PROSTVAC treatment	PROSTVAC treatment for 6 months with an additional optional year of maintenance for eligible patients
B	Delayed PROSTVAC treatment	Surveillance for 6 month followed by PROSTVAC treatment for 6 months with an additional year of maintenance for eligible patients

Randomization and Arm Assignment

Subjects in Cohort 1 will be randomized on a 1:1 basis to **Arm A** or to **Arm B**. The computerized randomization will be performed by the NCI Central Registration Office. CRO staff will send a secured e-mail with the Verification of Registration of the patient and treatment arm patient is randomized to. This process will be completed within 15–30 minutes of sending the eligibility checklist. CRO will keep track of all randomization data in Clinical Data Registry (CDR) of CRO.

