As an additional secondary exploration, using all 36 patients on the surveillance arm, the fraction that experiences a 50% decline relative to the time of starting vaccine will be determined. Using an exact binomial test, 36 patients will have 79% power to test whether the fraction exceeds a null fraction of 30% and is consistent with 50% who have 50% declines, with a one-tailed 0.05 alpha level test. In practice, the fraction with a 50% decline will have a 95% confidence interval created about the result in order to describe what values it would be consistent with. Exploratory analyses will also be performed to compare the growth rate changes at additional time points, such as 10 and 12 months.

Immune response generated by prostvac will also be evaluated and will be compared to the fraction of patients on the two arms who have a substantial T cell response as measured by exposure to overlapping PSA peptides. The patients will be considered to have had a T cell response if there is at least a 2 fold increase in immune response compared to baseline. This response is expected to be minimal during the first 6 months on the surveillance arm and more pronounced on the arm receiving Prostvac initially. With 36 patients per arm, there is 80% power to detect a difference between 10% with immune response on the surveillance arm and 40% on the Prostvac arm, with a two-sided 0.05 significance level using Fisher's exact test. Should only 29 patients per arm have evaluable immune response data, there would be 81% power to detect a difference between 10% and 45% with immune responses.

Other secondary endpoints include performing immune response evaluation including CD4 cells, CD8 cells, PSA-specific T-cells, natural killer cells, Regulatory T-cells, Regulatory T-cell function, cytokines, and naïve thymic emigrants; and associating immunologic outcomes with PSA responses/changes in growth rates. (This could be done every 6 months). Each of these endpoints will be analyzed using appropriate nonparametric methods when applicable and the results from these analyses will be presented without formal adjustment for multiple comparisons, but in the context of the number of such evaluations undertaken.

Beginning with amendment G, patients enrolled onto either the immediate vaccine arm or the surveillance followed by vaccine arm will be asked to complete a prostate cancer specific QOL survey with 18 questions (MAX-PC) as well as the FACT-P survey at the following time points:

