- Please complete a transmittal form for each PBMC timepoint and include with sample shipment. Blank transmittal form will be provided. For batch-shipped serum, please provide an Excel spreadsheet manifest listing all included samples. Information that should be listed on the manifest includes Subject ID, Sample ID, Sample Type (i.e. serum), Collection Date/Time, Study Day, Number of Vials, and any Comments.

Shipping Supplies:

NCI does not provide lab kits/shipping supplies. Please send samples using generic ambient (PBMCs) and dry ice (serum) Category B sample shippers (such as EXAKT-PAK or equivalent).

EXAKT-PAK supplies available at:

<https://www.exaktpak.com/store/>

EXAKT Technologies, Inc.

Home office: [name]
[name]
[contact]

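### Sites tell the laboratory that runs the immune assays each patient's treatment schedule, and nothing in the plan keeps arm from the staff who gate the powered T-cell comparison

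*Combined protocol and SAP*

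**What the plan says.** - **Who runs the assays.** Section 1.2.4 assigns the immunologic studies for all patients to the Laboratory of Tumor Immunology and Biology (LTIB). Section 4.2 has specimens delivered there from the repository. In 1.2.4 the authors describe themselves as a group within LTIB.
- **What LTIB is told.** Section 4.1.4, which covers participating sites only, says that once the "treatment schedule has been determined, [name] at the Laboratory of Tumor Immunology and Biology/NIH should be notified". The stated reason is planning.
- **Coding.** Under Section 4.1.3 the repository discards the tube label and stores samples under unique identifiers, with the linking code held by NCI study personnel. Section 4.2 adds that the vial ID carries no patient information.
- **How a response is read.** Section 1.2.4 states: "Fluorescence minus one (FMO) controls are used for gating, and non-viable cells were excluded". Background and pre-therapy values are then subtracted, and a net count of at least 250 is scored positive. Section 8 instead defines a response as at least a two-fold increase from baseline.
- **What rests on it.** For groups of 36, Section 8 states that "there is 80% power to detect a difference between 10% with immune response on the surveillance arm and 40% on the Prostvac arm". The test named for this comparison is Fisher's exact test, two-sided at 0.05. The section expects little response under surveillance and more under immediate vaccine.
- **Masking.** No section says whether the staff who gate and score are masked to arm.

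**The concern.** The trial is open label. Vaccine starts at once in Arm A and after six months of surveillance in Arm B, so a patient's schedule gives away his arm. The laboratory that receives this information also produces the response data, and the protocol records in advance which arm it expects to respond.

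The T-cell comparison is the only secondary between-arm analysis with its own power statement; the other powered secondary analyses lie within the surveillance arm. Flow-cytometry gates are set by a person, and their position determines the count that is tested against the cut-off. If arm is known when gates are set, expectation could move borderline counts towards response in Arm A. The same calls could then enter the planned associations between immune response and PSA growth rate. Later analysis cannot undo this once the gates are fixed.

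**Working it through.** **1. Can arm reach the gating staff under the plan as written?**

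- *Schedule.* It goes to a contact at LTIB for participating-site patients. Nothing says that this contact does not gate, or keeps the schedule from those who do.
- *Code.* It is held by NCI study personnel. The study group places itself in LTIB, and no separation between code holders and assay readers is stated.
- *Linkage.* Subtracting pre-therapy values (1.2.4) and judging change from baseline (8) both require each man's vials to be linked across time. Nothing says that linkage happens after gates are fixed, or outside the laboratory.
- *Draw pattern.* Appendix F allows an optional fifth time point in Arm B. In Appendix C, the footnote on research-blood windows lists C1D1 for the surveillance arm but not for the immediate arm. A linked series can therefore point to the arm even without the schedule notice.

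So the route is open, but the documents do not show that it is used.

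**2. Reproducing the plan's own power.** Inputs from Section 8: n = 36 per arm, rates 10% and 40%, two-sided Fisher's exact test at 0.05. Allocation is from 2.3.2: "Subjects in Cohort 1 will be randomized on a 1:1 basis to" Arm A or Arm B. The exact calculation is

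P(reject) = Σᵢ Σⱼ Bin(i; 36, p_B) · Bin(j; 36, p_A) · 1[Fisher p(i, j) ≤ 0.05].

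- 10% v 40%, 36 per arm: 80.0% (stated 80%).
- 10% v 45%, 29 per arm: 81.1% (stated 81%).

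Both stated figures reproduce. Masking would change neither.

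**3. What differential calls would do.** *Assumption, not in the documents:* both arms have the same true rate p, and a fraction f of true non-responders in Arm A is called positive, with no miscalls in Arm B. Arm A's apparent rate is then p + (1 − p)·f. For p = 10%:

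- f = 5%: 0.10 + 0.90 × 0.05 = 14.5%
- f = 10%: 0.10 + 0.90 × 0.10 = 19.0%

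Chance of p ≤ 0.05 with 36 per arm:

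| f | true rate 10% | true rate 20% |
|---|---|---|
| 0 | 1.4% | 2.6% |
| 5% | 3.9% | 3.9% |
| 10% | 11.2% | 7.7% |
| 15% | 23.6% | 14.5% |
| 20% | 39.6% | 24.3% |

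At a true rate of 10%, the part of this chance that favours Arm A is 0.7%, 3.7% and 11.2% for f = 0, 5% and 10%.

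**4. Scope of the notice.** The table applies f to every Arm A patient. If only a share s is affected, the effective fraction is s·f. The documents do not give s. With s = 50%, taken only as an example, a 10% miscall rate acts like f = 0.5 × 10% = 5%, and the chance is 3.9% rather than 11.2%.

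**The case against.** A reader might infer that every man's T-cell result is scored with his arm known, and that the notice defeats the coding of the vials. The documents do not support either reading.

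- The notice covers participating-site patients. No such instruction exists for patients at the NIH Clinical Center.
- It goes to one contact for planning. Nothing says that this person gates, or passes the schedule to those who do.
- Knowing a patient's schedule does not identify a coded vial. The reader would also need the code, and no section says that readers have it.
- Appendix F might be cited as further disclosure: "Information that should be listed on the manifest includes Subject ID, Sample ID, Sample Type (i.e. serum), Collection Date/Time, Study Day". That manifest accompanies batched serum sent to the repository. The gated assay uses blood mononuclear cells, which travel with a separate form, so the manifest does not show that gating staff see the study day.
- Background subtraction and the responder rule are arithmetic in both 1.2.4 and Section 8. Only gate placement is discretionary, and it is constrained by FMO controls.
- The miscall rates are assumed. At 5%, the chance of p ≤ 0.05 is 3.9%, still under the nominal 5%, because Fisher's test is conservative here.

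All of this stands, and it narrows the point. It does not remove it. The coding is described as a confidentiality measure, not as masking of assessors. The code holders are not separated from the laboratory, and scoring requires linkage that the plan does not place after gating. Table 1 in 1.2.4 does not settle how much gating matters. It shows counts near the 250 cut-off, such as 274 and 323, but as far as the broken table can be read those men also have larger counts, and counts below the cut-off are not shown.

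**Conclusion.** The concern holds in a limited form: the plan does not protect gate placement in the T-cell assay from knowledge of arm, and for participating-site patients it sends arm-revealing information to the laboratory that runs that assay. Whether any reader gates with the arm known cannot be determined from the documents.

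The size depends on an assumed miscall rate. With a true 10% response in both arms and 36 per arm, the chance of p ≤ 0.05 goes from 1.4% to 3.9% at 5% miscalls and 11.2% at 10%, so it passes the nominal 5% somewhere between those two rates. These figures take every Arm A patient as affected; if only some are, the effect is smaller.

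The stated power is correct and the primary PSA growth-rate comparison is untouched. This is a cheap improvement to a secondary endpoint.

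**What to change.** - **Section 4.1.4 and the matching text in Appendix F.** Planning notices give expected shipment dates only, and go to the repository or to a coordinator who does not gate.
- **Section 1.2.4 or 4.1.2, for patients at all sites.** State that gating is done on coded vials by staff who have neither the code, the treatment schedule nor the arm. State that gates and counts are locked before codes are linked to arm and visit, and that baseline subtraction and the responder call follow that linkage.
- **Responder rule.** Since the call would be made from locked counts, say which rule the Fisher comparison uses: the net count of 250 in 1.2.4 or the two-fold increase in Section 8.

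The cost is a few sentences and use of the coded inventory that already exists. The laboratory loses some advance planning information, and there is one added data-handling step. If the laboratory already works this way, only the wording changes. Sample size and stated power are unaffected.

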4.2 SAMPLE STORAGE, TRACKING AND DISPOSITION

The Clinical Support Laboratory, Leidos Biomedical Research, Inc.-Frederick, processes and cryopreserves samples in support of IRB-approved, NCI clinical trials. All data associated with the patient samples is protected by using a secure database. All samples drawn at the NIH Clinical Center will be transported to the NCI Frederick Central Repository by couriers.

Samples will be tracked and managed by Central Repository database. All samples will be stored in either a -20°C or -80°C freezer. These freezers are located at NCI Frederick Central Repository in Frederick, Maryland.

NCI Frederick Central Repositories store, among other things, biological specimens in support of NIH clinical studies. All specimens are stored in secure, limited-access facilities with sufficient security, backup, and emergency support capability and monitoring to ensure long-term integrity of the specimens for research.

Sample data is stored in the BioSpecimen Inventory System II (BSI). This inventory tracking system is used to manage the storage and retrieval of specimens, as well as to maintain specimen data. BSI is designed for controlled, concurrent access. It provides a real-time, multi-user environment for tracking millions of specimens. The system controls how and in what order database updates and searches are performed. This control prevents deadlocks and race conditions. For security, BSI has user password access, 3 types of user access levels, and 36 user permissions (levels of access) that can be set to control access to the system functions. BSI provides audit tracking for processes that are done to specimens including shipping, returning to inventory, aliquoting, thawing, additives, and other processes. BSI tracks the ancestry of specimens as they are aliquoted, as well as discrepancies and discrepancy resolution for specimens received by the repository. If a specimen goes out of the inventory, the system maintains data associated with the withdraw request. Vials are labeled with a unique BSI ID which is printed in both eye-readable and bar-coded format. No patient-specific information is encoded in this ID.

Investigators are granted view, input, and withdraw authority only for their specimens. They may not view specimen data or access specimens for which they have not been authorized. Access to specimen storage is confined to repository staff. Visitors to the repositories are escorted by repository staff at all times.

Samples will be used for research analysis, including immunologic monitoring as outlined in section **4.1.2**. All specimens for analysis will be requested from Leidos Biomedical, Inc. and will be delivered by Leidos Biomedical, Inc. couriers to the Laboratory of Tumor Immunology and Biology.

